3. INVESTIGATIONAL PLAN

3.1. Overall Study Design and Plan

This parallel, open-label study is designed to evaluate the comparative bioavailability of systemic copper exposure after insertion of VeraCept intrauterine contraceptive (IUD) vs ParaGard in post-menarcheal women. Up to 40 subjects will receive one of two treatments (A or B) as described below:

- Treatment A (N=20): VeraCept® IUD, test (referred to as VeraCept)
- Treatment B (N=20): ParaGard® IUD, reference (referred to as ParaGard)

[figure not shown]
Figure 3-1. Study Design Schemata – Treatment Comparison Phase

Subjects will be screened within 60 days prior to the first insertion of study drug, and blood samples will be collected within 28 days from first insertion of study drug at two visits within this screening period to establish baseline copper concentrations. At least 24 hours should separate each baseline sample. On Day 1 of each treatment period, PK, safety and baseline

assessments will be collected prior to IUD insertion. Subjects will return to the clinic at 48 hours post-IUD insertion (Day 3 (\pm 24 hours)) and on Days 8 (\pm 1 day), 15 (\pm 1 day), 22 (\pm 1 day), 29 (\pm 1 day) and 57 (\pm 3 days) for blood collection for measurement of total serum copper concentrations.

Figure 3-2. Study Design Schemata – Extension Phase

On Day 57, ParaGard subjects will exit the study and may continue ParaGard use per standard clinical care. VeraCept subjects will continue in the extension phase of the study intended to assess long-term stability of serum copper concentrations up to 5 years and monitor safety. During the first 3 years, subjects will return to the clinic every 6 months for clinical assessments and blood collection for measurement of total serum concentrations. Following Year 3, subjects will return annually up to Year 5. During the extension phase, PK collections may occur anytime within 30 days of the planned collection time. Subjects prematurely discontinuing the study should follow the procedures specified in Section 6.1.7 Early Discontinuation Visit. Additional follow-up visits may be scheduled, as needed, if a subject has an ongoing significant adverse event (AE) and/or a clinically significant laboratory abnormality. A schedule of the study procedures and assessments to be conducted for each subject is provided in the Time and Events Table (Appendix 1).

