4.4. Removal of Subjects from Therapy/Premature Discontinuation

Subjects will be encouraged to complete the study and all assessments. A subject will be discontinued from the study for the following medical or administrative reasons:

- Occurrence of a treatment-emergent AE that represents an unacceptable risk to the subject and continued participation in the investigational study is not warranted per judgment of the Investigator. The Investigator must follow the subject until the AE resolves or satisfactorily stabilizes;
- Pregnancy;
- Sponsor decision;
- Subject request; and/or
- Non-compliance with the protocol.

The Investigator may discontinue individual subjects from the study at any time. Subjects may voluntarily withdraw at any time. The reason(s) for subject not completing the study will be recorded. Where subjects are “lost to follow-up”, the site should make every attempt to contact the subject (3 telephone calls and if necessary, a certified letter to the subject’s mailing address) so that they can be appropriately withdrawn from the study.

For subjects that fail to attend a required visit, the site should attempt to contact the subject and re-schedule the missed visit as soon as possible. If a subject fails to attend 2 or more visits as scheduled, the subject may be discontinued per agreement between the Sponsor and the Principal Investigator.

If subjects prematurely discontinue the study, additional subjects may be enrolled as replacement subjects (and assigned to the same treatment) at the discretion of the Sponsor in consultation with the Investigator.

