6.1.5. Months 6, 12, 18, 24, 30, 36, and 48 (± 30 days)

- Vital signs and weight
- PK sample collection
- Pelvic exam to confirm IUD placement/string check
- Transvaginal ultrasound, if clinically indicated to confirm adequate IUD placement
- Prior and concurrent medication
- Adverse events
- Subject education including:
 - Concomitant contraception - if there are concerns that the IUD is not properly placed, counsel the subject on the need for additional contraception

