4.1.4 Analysis Windows

For analysis purposes, early termination visits and unscheduled follow-up visits will be assigned analysis visits according to the analysis windows in the following table. This mapping applies to labs, vital signs, and all other data planned to be collected and analyzed by visit in the Study Data Tabulation Model (SDTM) finding domains. Where multiple measurements for a particular parameter appear within an analysis window, the result closest to target day will be used. If equidistant, the latter result will be used for the summary measure. All measures may not be used in the data summaries (e.g., 2 vital signs measures within the same analysis visit window), but all measurements will appear in the datasets and listings.

Table 4.1.4.1 Analysis Windows:

Scheduled Visit (Subject Visit Window)	Analysis Visit	Analysis Window Target Day	Analysis Window	
			Lower Bound	Upper Bound
Visit 1/Screening	Baseline	1	N/A	1
Visit 2 (Day 1)				
Visit 3 (Day 3± 24 hours)	Day 3	3	2	5
Visit 4 (Day 8± 1 day)	Day 8	8	6	11
Visit 5 (Day 15± 1 day)	Day 15	15	12	18
Visit 6 (Day 22± 1 day)	Day 22	22	19	25
Visit 7 (Day 29± 1 day)	Day 29	29	26	43
Visit 8 (Day 57± 3 days)	Day 57	57	44	120
Visit 9 (Month 6± 30 days)	Month 6	182	121	273
Visit 10 (Month 12± 30 days)	Month 12	364	274	456
Visit 8 (Month 18± 1 month)	Month 18	548	457	639
Visit 9 (Month 24± 1 month)	Month 24	730	640	822
Visit 10 (Month 30± 1 month)	Month 30	913	823	1004
Visit 12 (Month 36± 1 month)	Month 36	1095	1005	1278
Visit 14 (Month 48± 1 month)	Month 48	1460	1279	1642
Visit 16 (Month 60± 1 month)	Month 60	1825	1643	N/A

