4.1.5 Exposure Periods

The first exposure cycle starts on Day 1 of successful study device insertion. A full exposure cycle is comprised of 28 days. One woman-year comprises thirteen 28-day cycles. The following exposure periods are defined for analysis in terms of planned study days and study cycles to facilitate the efficacy and certain safety analyses.

Exposure Period	Study Day of Period Start (PSTDY)	Study Day of Period End (PENDY)
Year 1 (Cycle 1- Cycle 13)	1	364
Year 2 (Cycle 14-Cycle 26)	365	728
Year 3 (Cycle 27-Cycle 39)	729	1092
Year 4 (Cycle 40-Cycle 52)	1093	1456
Year 5 (Cycle 53-Cycle 65)	1457	1820
First 2 Years (Cycle 1-Cycle 26)	1	728
First 3 Years (Cycle 1-Cycle 39)	1	1092
First 4 Years (Cycle 1-Cycle 52)	1	1456
5 Years (Cycle 1-Cycle 65)	1	1820

Type of Events and Study Day During an Exposure Period

ETYPE	Event	Study Day of Event (EVTDY)
A	Expulsion	Study Day of Expulsion date
B	Expulsion followed by conception within 7 days	Study Day of Expulsion date
C	Removal	Study Day of Removal date
D	Removal followed by conception within 7 days	Study Day of Removal date
E	Pregnancy before expulsion	Study Day of Conception date
F	Pregnancy before removal	Study Day of Conception date
H	Lost to follow-up without pregnancy, expulsion, or removal	Study Day of Last Date Device in Situ
I	Complete period without pregnancy, expulsion, or removal	Study Day of Period End Date

Note: Removal due to partial expulsion will be treated as expulsion

Exposure Duration in Days (EXDUR):

if EVTDY-PSTDY>0 then EXDUR = min(EVTDY-PSTDY+1, PENDY-PSTDY+1);
 else EXDUR=.;

Exposure Duration in Cycles (NCYCF) = EXDUR/28

Number of Completed Cycles (NCYCC) = INT(NCYCF)

Number Relevant Cycles (NCYCR)

=NCYCC+1 if last partial cycle is \geq 23 days
 =NCYCC+1 if last partial cycle ETYPE is B, D, E, or F
 =NCYCC, otherwise.

Number of Evaluable Cycles (NCYCEV) =NCYCR

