4.11.5 VeraCept Expulsion Rates

Cumulative VeraCept Expulsion Rates for Years 1 through 5 will be estimated via Kaplan-Meier method for the Safety population. The complementary log-log transformation will be used to construct 95% CIs.

VeraCept expulsion includes both total expulsion and partial expulsion. Total expulsion is defined as cases in which VeraCept is observed in the vagina, not shown in the uterus by ultrasound, or if the women confirmed expulsion. Partial expulsion cases are defined as when

VeraCept is visible in the cervical canal by gynecologic exam or ultrasound. If partially expelled VeraCept is removed, the removal will be considered an expulsion event for this analysis.

- Time to expulsion in cycles will be defined as time to total expulsion discovered or removal of the partially expelled VeraCept from the date of successful insertion
- Removal of VeraCept for any other reason will be censored at the removal cycle.
- If a subject discontinued because of pregnancy, the subject will be censored at the cycle of conception
- Lost-to-follow-up will be censored at the last cycle where VeraCept is in Situ, defined as the date the subject was deemed lost to follow-up as entered on the Study Exit Status CRF page.
- Those with VeraCept still in place for protection at the end of exposure period will be censored at the end of exposure period.

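### Women lost to follow-up are censored for expulsion at the date they were deemed lost, not when the device was last known in place, so the Kaplan-Meier expulsion rate can only be equal to or lower than it should be

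*SAP*

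**What the plan says.** Safety SAP 4.11.5 plans cumulative VeraCept expulsion rates for Years 1 to 5 by Kaplan-Meier in the Safety population, with 95% complementary log-log intervals. It censors lost women at "the last cycle where VeraCept is in Situ, defined as the date the subject was deemed lost to follow-up", with the date taken from the Study Exit Status CRF page. An expulsion counts when the device is seen in the vagina or is not shown in the uterus on ultrasound, "or if the women confirmed expulsion". A partially expelled device that is removed also counts. Total expulsions are timed to discovery.

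For exposure, safety SAP 4.1.5 (event type H) gives lost women a different label, "Study Day of Last Date Device in Situ". It neither defines the term nor ties it to the deemed-lost date.

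Protocol 4.4 says how a woman comes to be withdrawn as lost: "the site should make every attempt to contact the subject (3 telephone calls and if necessary, a certified letter" to her mailing address. It also allows discontinuation after two or more missed visits.

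The device is checked at visits. Protocol 6.1.5 lists "Pelvic exam to confirm IUD placement/string check" at each extension visit. Visits are six-monthly for three years, and then Protocol 3.1 says: "Following Year 3, subjects will return annually up to Year 5".

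**The concern.** The label and its definition point to different dates. The last cycle in situ is when someone last knew the device was there. The deemed-lost date records when the site gave up. Nothing in the documents makes the two equal, and with visits 6 to 12 months apart they can differ by many cycles.

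In that interval an expulsion in the lost woman cannot become an event, because events are timed to discovery and she is not being seen. She still counts in the denominator for every expulsion observed in other women. The error runs in one direction and favours the device. Expulsion is an adverse event of specific interest in this study, and Protocol 1.1 presents fewer expulsions as a benefit of the design. With about 20 VeraCept women, a few losses can move the estimate.

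**Working it through.** The plan states no expulsion or loss rate, so there is no figure of its own to reproduce. The check covers gap length, direction and size.

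**Gap length.** Inputs are the target days in safety SAP 4.1.4 and the 28-day cycle in 4.1.5. The next missed visit is taken as the earliest point at which a woman could be deemed lost.

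| Last seen | Next visit | Gap in cycles |
|---|---|---|
| Day 57 | Month 6 (day 182) | (182 − 57)/28 = 4.5 |
| Month 6 | Month 12 (day 364) | (364 − 182)/28 = 6.5 |
| Month 36 (day 1095) | Month 48 (day 1460) | (1460 − 1095)/28 = 13.0 |

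Intervals from Month 12 to Month 36 are also about 182 days. Time spent on contact attempts is extra and is not stated. If a woman were dropped only after two missed visits, the gap from Month 36 would be (1825 − 1095)/28 = 26.1 cycles.

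**Direction.** The estimated rate is 1 − S(t), with S(t) the product of (1 − d_j/n_j) over expulsion times. With the observed expulsions fixed, moving a censoring time later leaves every d_j unchanged and can only keep or raise n_j. So 1 − S(t) can only stay equal or fall. In 20,000 random data sets of 20 women, each read at cycles 13, 26, 39, 52 and 65 (100,000 comparisons), the rate under deemed-lost censoring was higher in 0, equal in 40,008 and lower in 59,992.

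**Size, under assumed inputs.** Take 20 women and 2 observed expulsions. All lost women are assumed to have gaps covering the same expulsion or expulsions.

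| Expulsions inside the gap | Lost | SAP rule | Last known in place |
|---|---|---|---|
| None | any | 10.0% | 10.0% |
| One (the other at cycle 2) | 2 | 1 − (19/20)(18/19) = 10.0% | 1 − (19/20)(16/17) = 10.6% |
| One (the other at cycle 2) | 5 | 10.0% | 1 − (19/20)(13/14) = 11.8% |
| Both | 2 | 1 − 18/20 = 10.0% | 1 − 16/18 = 11.1% |
| Both | 5 | 10.0% | 1 − 13/15 = 13.3% |

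A heavier assumed case has 3 expulsions at cycles 1, 6 and 9, with k women last seen at Day 57 and deemed lost at least 7 cycles later. The SAP rule gives 1 − 17/20 = 15.0%. Last-known-in-place censoring gives 1 − (19/20)(17 − k)/(19 − k), which is 16.2% for k = 2 and 22.3% for k = 8.

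**The case against.** Four objections deserve an answer.

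- **The CRF field.** The date comes from the Study Exit Status page, which is not in the documents. Sites may enter the last contact date there, in which case the gap shrinks. That is possible, but the SAP calls it the date deemed lost. If last contact is meant, the sentence still needs correcting.
- **The alternative is not free of bias.** A woman can report an expulsion between visits. Censoring at her last visit removes time in which she could still have reported one, which pushes the rate up. This is partly right. In a simulation with an assumed true five-year rate of 10% and 40% lost, last-visit censoring gave 9.9% to 10.0% when expulsions were found at visits. It gave 10.2% to 10.4% when all were self-reported at once. The SAP rule gave 9.4% to 9.8% throughout. Accepting documented contacts as well as visits narrows the upward error, and a deemed-lost sensitivity analysis brackets it.
- **Precision.** For 2 expulsions in 20 women, the planned 95% interval is 2.6% to 34.4%, so a shift of up to 3.3 points is small beside it. The table's larger figures also need all the gaps to overlap the same expulsions, and staggered losses would give less. Both points stand and limit the importance. A wide interval does not cancel a bias of known sign.
- **Other outputs.** Yearly expulsion counts (4.9.1.2), disposition by interval (4.5) and examination listings (4.11.9) let a careful reader reconstruct what happened. They do not correct the reported rate.

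**Conclusion.** The concern holds. As written, 4.11.5 counts time with unknown device status as expulsion-free, and the rate can only be equal to or lower than with last-known-in-place censoring. The direction is certain given the observed expulsions. The size is not known, because the documents give no losses, expulsion times or actual gap lengths. The difference is zero when no observed expulsion falls inside a lost woman's gap. In the assumed examples it reaches 3.3 points with 2 expulsions and 5 women lost, and 7.3 points with 3 expulsions and 8 lost.

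Event type H in 4.1.5 is an ambiguity, not an established error. Evaluable cycles would be inflated only if the deemed-lost date were carried into it, and the text does not say that it is. The expulsion analysis is descriptive and the primary PK endpoints are untouched, so this should be corrected but does not threaten the main result.

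**What to change.** In 4.11.5, replace the deemed-lost definition with the date of the last visit or documented contact at which the device was known to be in place, by string check, pelvic examination, ultrasound or the woman's own report. Her report has to be accepted because the event definition accepts it; events and censoring then rest on the same sources. Define the event type H term in 4.1.5 in the same words. Keep the deemed-lost date as a sensitivity analysis.

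The text change is one sentence and one definition. Placement checks are already scheduled at every visit from Day 8. Documented contacts between visits may have to be taken from site records, and the programs need some rework. SAP version 2.0 was aligned with existing table shells and a Year 3 analysis is planned, so tables may already exist under the current rule; the sensitivity analysis keeps them comparable. The reported expulsion rate may become slightly less favourable.

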4.11.6 Vital Signs and Weight

The observed values and changes from baseline in the following vital signs and weight parameters will be summarized by visit for the Safety population:

- Systolic blood pressure (mm Hg)
- Diastolic blood pressure (mm Hg)
- Pulse rate (bpm) sitting
- Respiration rate (breaths/min)
- Body temperature
- Body weight (kg)
- BMI (kg/m^2)
- BMI (underweight, normal, overweight, obese)

Vital signs, weight, and BMI will be included in a data listing.

4.11.7 Physical Examination

Physical examination includes examination of general appearance; skin; head, eyes, ears, nose, and throat; thyroid; lungs; back; breasts; heart; abdomen; extremities; and neurological system.

4.11.8 Physical examination results indicating significant abnormalities will be presented in a data listing. Pregnancy Results

All pregnancy testing data will be presented in the listings.

Pregnant subjects with clinical outcome data including infant abnormalities will be presented in the listings.

4.11.9 Pelvic Examination and Transvaginal Ultrasound

All pelvic examination and transvaginal ultrasound data will be presented in a data listing.

5 CHANGES FROM PROTOCOL

The pearl index based on safety cycles was added as a measure of the contraceptive efficacy. The reference product labeling was updated after the study initiated and removed capitalization of the G.

6 REFERENCES

1. Salwen, M.J., *Vitamins and Trace Elements* 23 ed. Henry's Clinical Diagnosis and Management by Laboratory Methods, 23rd Edition. 2017, St. Louis, Missouri: Elsevier Health Sciences. 1700.

Table 1: Study Schedule of Assessments

Visit	Screening	Enrollment/IUD Placement	Clinic PK visits		Clinic PK visits (VeraCept Subjects ONLY)	Month 60 OR Exit Visit
Day	Day -28 to 1	Day 1	Day 3 (±24 hrs)	Days 8, 15, 22, 29 (±1 day) Day 57⁶ (±3 days)	Months 6, 12, 18, 24, 30, 36 and 48 (±30 days)	Month 60 (±30 days) OR Exit Visit
Assessment of Eligibility	X	X				
Distribution of subject materials (if applicable)	X					
Informed Consent/Assent/PHI and Bill of Rights	X					
Demographics and baseline characteristics	X					
Medical/surgical, gynecologic, and menstrual history	X					
Vital signs and weight	X	X	X	X	X	X
Height	X					
General physical exam	X					
Pelvic exam (string check if post IUD insertion)	X	X ¹		X	X	X
Cervical cytology	X					
Cervical infection tests	X ^{2,3}					
Transvaginal, ultrasound, only if clinically indicated		X		X	X	X
Pregnancy test – urine	X	X				X
Prior and concurrent medication	X	X	X	X	X	X
Adverse events	X	X	X	X	X	X
IUD placement		X				
IUD removal						X ⁷
Concomitant contraception		X				X
Subject education – need for contraception	X	X	X	X	X	X
Blood draw for PK analysis (serum copper sample)	X ⁴	X ⁵	X ⁵	X ⁵	X ⁵	X ⁵

Footnotes

1. Pelvic exam for IUD string check by palpation or visualization.
2. Screening for cervical infection tests are to be done at screening unless these tests have been previously completed within 3 months of the screening visit and were negative. If a subject tests positive prior to IUD insertion, the subject should be treated prior to IUD placement. The subject may be inserted 7 days post-treatment. A cervical infection retest should be done 3-months post-IUD insertion to assure there is not a case of re-infection.3a. This first e-diary review, prior to VeraCept placement, to be used as training with the subject. This diary data is not part of data collection or analysis. It is intended to ensure the subject understands how to complete the diary and determine subject compliance throughout e-diary collection.
3. Insertion can occur without receipt of test results if there is no clinical evidence of infection. If, after IUD insertion, the screening cervical infection test results are positive, the subject should be treated. A cervical infection retest should be done 3 months post-treatment.
4. Subjects will be screened within 60 days prior to the first insertion of study drug, , and two blood samples will be collected within 28 days from Day 1, and at least 24 hours apart within this screening period (can be performed on Screening and Day 1 visit prior to IUD insertion). to establish baseline copper concentrations.
5. On Day 1, collect blood samples for pharmacokinetic analysis prior to intrauterine insertion. On Day 3, collect samples 48 hours \pm 24 hours after IUD insertion. PK samples on Day 8, 15, 22, and 29 should be collected within 1 day of the planned collection day while Day 57 should be collected within 3 days of planned collection day, at approximately the same time as the Day 3, 48-hr \pm 1 day PK sample collection. Following the PK collections on Day 57, the PK samples should be collected within 30 days of the planned collection day.
6. Paragard subjects will have Exit Visit procedures completed on Day 57.
7. Paragard subjects may continue Paragard use per standard clinical care or have the device removed.
